A proof of concept clinical trial evaluating the safety and efficacy of Eucrisa (crisaborole) in patients with mild to moderate seborrheic dermatitis

Study Protocol & Statistical Analysis Plan

NCT03567980

March 6, 2018

[name]., Principal Investigator
University of Alabama at Birmingham
Birmingham, AL 35294

A proof of concept clinical trial evaluating the safety and efficacy of Eucrisa (crisaborole) in patients with mild to moderate seborrheic dermatitis

Co-Investigators: [name], [name], DNP, and [name]

Site: University of Alabama at Birmingham

Background

Seborrheic dermatitis is a common and recurrent dermatosis that characteristically involves the scalp, nasolabial folds, eyebrows, glabella, and upper eye lids. It presents as an erythematous, thin scaly patch with a greasy sandpaper texture that varies depending on disease severity. While seborrheic dermatitis most frequently occurs on the face, it can involve other areas of the body especially the chest, abdomen, and naval. Overall incidence is thought to be between 2-5% of the general population, though this is likely an underestimation. Pruritus is variable, though the signs and symptoms of this disorder are certainly worsened by certain external conditions especially weather, personal perspiration, stress, and poor hygiene^{i, ii, iii}. Patients often complain about the red, scaly patches on the face.

Antifungal agents are frequently used as monotherapy or in combination regimens in the treatment of seborrheic dermatitis. Topical corticosteroids are often used for their anti-inflammatory effects. Long term use of topical steroids on the face is not a preferred treatment modality due to the risk of striae development and other textural changes that occur over time. Therefore, topical crisaborole may be an alternative given its non-corticosteroid anti-inflammatory action. Crisaborole is a phosphodiesterase-4 (PDE-4) inhibitor that increases intracellular cyclic AMP (cAMP) levels to exert its anti-inflammatory effects. While it has not previously been investigated for its effects in seborrheic dermatitis, further studies evaluating its role in this disease are warranted.

Therefore, we propose a proof of concept study using topical crisaborole 2% ointment on the face for 4 weeks to evaluate the anti-inflammatory action of this agent and its utility in the treatment of facial seborrheic dermatitis.

Primary Outcome Measure:

- ISGA will be collected via skin examination to evaluate efficacy of Crisaborole 2% topical ointment in the treatment of seborrheic dermatitis. A 0 or 1 (clear or almost clear) on the ISGA would be considered a treatment success

Secondary Outcome Measure:

- The Itch NRS will be collected to assess the percentage of improvement of patient reported itching. This will be calculated as a percent changes from baseline in the Itch NRS scale.

Safety Outcome Measures

- Incidence, severity, and type of treatment-emergent adverse events will be collected via the local tolerability assessment
- Vital signs, clinical assessments, and laboratory test results
- Concomitant medication use
- Adverse events

Primary Objective

- To assess the efficacy of crisaborole ointment 2% (Eucrisa) in the treatment of mild to moderate seborrheic dermatitis.

Statistical Analysis

As this is a proof of concept, open label study, descriptive statistics will be utilized. The goal is for the information to yield data points robust enough to be accepted in a high impact, peer reviewed journal. The sample size was based known patient population and pragmatic considerations and is adequate to characterize anticipated observed effects.

Study Design

40 eligible subjects will be enrolled

Inclusion criteria

1. Capable of understanding and willing to provide signed and dated written voluntary informed consent before any protocol specific procedures are performed.
2. Male or female subjects 18 to 70 years of age.
3. Able to complete the study and to comply with study instructions.
4. Female subjects of childbearing potential must have a negative pregnancy test. Sexually active women of childbearing potential participating in the study must agree to use a medically acceptable form of contraception (which includes oral contraception, injectable or implantable methods, or intrauterine devices) during the entire duration of the study
5. Mild to moderate seborrheic dermatitis on the face with an ISGA of 2 or 3 at baseline.

Exclusion criteria

1. Use of systemic antifungal agents, corticosteroids or other immunosuppressive therapies, or systemic retinoids within 4 weeks prior to the baseline visit.

2. Use of topical antifungal therapy, corticosteroid therapy, or calcineurin inhibitors to the face, within 2 weeks prior to the baseline visit. Topical, over-the-counter antifungal shampoo will be allowed as long as it has remained constant for 4 weeks prior to baseline.
3. Use of any investigational drugs within 4 weeks prior to the baseline visit, or subjects scheduled to receive an investigative drug other than the study product during the period of the study.
4. History of known or suspected intolerance to any of the ingredients of the study product.
5. Female subjects who are pregnant, trying to become pregnant or lactating.
6. Any clinically relevant abnormal vital signs or findings on the physical examination which in the opinion of the investigator might interfere with the study assessments.
7. A clinically relevant history of abuse of alcohol or other drugs.
8. Any major illness within 30 days prior to the baseline visit.
9. Subjects with any clinically significant condition which would, in the opinion of the investigator, compromise the subject's participation in the study.
10. Subjects who are immunocompromised (ex: HIV).
11. Considered unable or unlikely to attend the necessary visits.
12. Currently using any medication, which in the opinion of the investigator may affect the evaluation of the study product
13. Subjects who have significant neurological conditions (Parkinson's disease or Stroke), who in the opinion of the investigator are not eligible for the study due to the severity of neurological condition.
14. Subjects with a history of non-melanoma skin cancer of the face within 6 months

Procedures:

After the informed consent process, the subject will be evaluated for facial seborrheic dermatitis utilizing the Investigator's Static Global Assessment (ISGA). The subject must have a ISGA score of 2 or 3 to qualify for the study.

Patient reported outcomes will be collected at baseline and week 4. We will utilize the SkinDex29 and Itch NRS.

Provider and Patient local tolerability assessment will be collected at Baseline (before medication application) week 1, 2, and 4. We will assess for redness, pain, burning, and scaling at the application site.

Adverse events will be collected from after the informed consent document is signed through week 4.

Concomitant medications will be collected from screening to week 4.

Subjects can continue to use their over-the-counter dandruff shampoo as long as it has remained constant for the past 4 weeks. Subjects will be instructed to avoid the facial area with the shampoo.

Subjects may continue their established makeup, moisturizer and sunscreen regimen.

Other than Urine Pregnancy Tests for women of childbearing potential, no other laboratory evaluations are necessary.

Patients will be instructed to apply a thin layer of medication to the affected area on the face twice daily for 4 weeks, and they will be advised that the medication is not for ophthalmic, oral, or intravaginal use.

Procedures are listed in table below.

Schedule of Events

	Scr	BL	Wk1	Wk 2	Wk 4
Informed Consent	x				
Inclusion/Exclusion Criteria	x	x			
Med History	x				
PE	x				x
Investigator Static Global Assessments (ISGA)	x	x	x	x	x
Seborrheic dermatitis grading scale	x	x	x	x	x
Photography	x	x	x	x	x
UPT	x				x
Con Meds	x	x	x	x	x
AE		x	x	x	x
SkinDex 29		x			x
Itch NRS		x			x
Patient and Provider Tolerability Assessment		x	x	x	x

ⁱ Katsambas A, Antoniou C, Frangouli E, Avgerinou G, Michailidis D, Stratigos J. A double-blind trial of treatment of seborrheic dermatitis with 2% ketoconazole cream compared with 1% hydrocortisone cream. *Br J Dermatol*. 1989 Sep;121(3):353–7.

ⁱⁱ Piérard-Franchimont C, Piérard GE, Arrese JE, De Doncker P. Effect of ketoconazole 1% and 2% shampoos on severe dandruff and seborrheic dermatitis: Clinical, squamometric and mycological assessments. *Dermatology*. 2001;202(2):171–6.

ⁱⁱⁱ Stratigos JD, Antoniou C, Katsambas A, Böhler K, Fritsch P, Schmölz A, et al. Ketoconazole 2% cream versus hydrocortisone 1% cream in the treatment of seborrheic dermatitis. A double-blind comparative study. *J Am Acad Dermatol*. 1988 Nov;19(5 Pt 1):850–3.

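### Does success at ISGA 0 or 1, with entry at ISGA 2 or 3, require a pre-specified report by baseline grade?

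*Combined protocol and SAP*

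**What the plan says.** The Primary Outcome Measure section defines response by the end state alone: "A 0 or 1 (clear or almost clear) on the ISGA would be considered a treatment success". It sets no minimum change from baseline and names no visit.

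Inclusion criterion 5 requires "Mild to moderate seborrheic dermatitis on the face with an ISGA of 2 or 3 at baseline", and the Procedures section repeats it: "The subject must have a ISGA score of 2 or 3 to qualify for the study".

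The Statistical Analysis section gives the method in one sentence: "As this is a proof of concept, open label study, descriptive statistics will be utilized". It adds that the results should be "data points robust enough to be accepted in a high impact, peer reviewed journal". It names no subgroup, stratified summary or shift table.

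Under Study Design, "40 eligible subjects will be enrolled", with no quota or cap for either baseline grade. The Background section describes "topical crisaborole 2% ointment on the face for 4 weeks". The Schedule of Events marks ISGA at screening, baseline and weeks 1, 2 and 4.

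**The concern.** One success rule is applied to two starting points. A move from 2 to 1 counts as success; a move from 3 to 2 is the same size and counts as failure. If mild subjects reach the target more easily, one overall rate could consist largely of one-grade changes, scored by an unblinded investigator with no comparator described. The rate would also depend on how many mild subjects happened to enrol.

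The primary objective is efficacy across mild to moderate disease, and the sponsor hopes to publish in a leading journal. A reader could take a respectable overall figure as evidence of benefit in both grades when it came almost entirely from one. Choosing the breakdown after unblinded data have been seen would also be less credible than naming it beforehand.

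**Working it through.** **Inputs from the documents.** Success is ISGA 0 or 1; entry is ISGA 2 or 3; N = 40; analysis is descriptive; ISGA is recorded at baseline and at weeks 1, 2 and 4. The sample size is described as pragmatic, with no response rate, alpha or power, so the plan has no figure of its own to reproduce.

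**Step 1: grades needed.** From 2 to 1 is 2 − 1 = 1 grade. From 3 to 1 is 3 − 1 = 2 grades. The asymmetry follows directly from the two rules.

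**Step 2: what an overall rate can hide.** Assume 20 subjects per baseline grade (the documents give no split). Exact (Clopper-Pearson) 95% limits for x successes in n are the 2.5% point of Beta(x, n − x + 1) and the 97.5% point of Beta(x + 1, n − x).

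| Pattern | Baseline 2 | Baseline 3 | Overall |
|---|---|---|---|
| Even | 9/20 = 45% (23.1 to 68.5) | 9/20 = 45% (23.1 to 68.5) | 18/40 = 45% (29.3 to 61.5) |
| Uneven | 16/20 = 80% (56.3 to 94.3) | 2/20 = 10% (1.2 to 31.7) | 18/40 = 45% (29.3 to 61.5) |

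The overall rate cannot tell these patterns apart. The uneven row is deliberately extreme.

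**Step 3: dependence on case mix.** Let s be the share entering at ISGA 2, and p2 and p3 the success rates by entry grade. The overall rate is s·p2 + (1 − s)·p3. All rates and shares below are assumptions.

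- p2 = 60%, p3 = 30%: at s = 0.25, 0.15 + 0.225 = 37.5%; at s = 0.75, 0.45 + 0.075 = 52.5%. The shift is 15 points.
- p2 = 40%, p3 = 30%: at s = 0.25, 0.10 + 0.225 = 32.5%; at s = 0.75, 0.30 + 0.075 = 37.5%. The shift is 5 points.
- p2 = p3: the shift is 0.

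Even the 15-point range, 37.5% to 52.5%, lies within the 29.3% to 61.5% interval for 18/40. With no comparator described, case mix cannot bias a between-group contrast. It matters only for carrying the rate over to another population or study.

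**Step 4: what a split would yield.** At an observed 50%, 20/40 has limits of 33.8% to 66.2%, and 10/20 has 27.2% to 72.8%. The half-width grows from about 16 to about 23 points. The split shows where responses sit; it cannot separate drug effect from regression to the mean or rater expectation. The documents give no rating error or severity distribution, so the number of successes to expect without any drug effect cannot be derived from them.

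**Step 5: does anything in the plan turn on this?** The plan contains no hypothesis test, success threshold or stopping rule based on the rate. A baseline-by-week-4 cross-tabulation is a descriptive statistic and needs no new data.

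**The case for a change.** The strongest case for acting is that in an uncontrolled, open-label study the within-group description carries the whole efficacy message, and the uneven row in the table shows that one number can mislead. The remedy is only wording: name week 4, report success by baseline grade with exact intervals, and add a shift table. Naming these before the data are seen also protects credibility.

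Part of this stands. The plan does not specify the breakdown, the table would be useful, and it would cost almost nothing.

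It does not show a defect. The harm requires that only an overall rate be reported, and the plan does not say that; its commitment to descriptive statistics leaves the by-grade table open. The overall ISGA 0/1 rate would remain the headline, with the same definition and value. The unnamed visit is a separate point of missing detail, and week 4, the end of a four-week treatment, is its natural reading.

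**Conclusion.** No change to the plan follows. The observation is correct: success takes one grade from ISGA 2 and two from ISGA 3, and no by-grade report is named. But the endpoint is a legitimate static one, nothing is decided on the rate, and a competent analyst would fill this gap with a simple shift table under the existing wording.

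The possible size rests wholly on assumed rates and case mix: a shift of 0 to 15 points in the overall rate in the examples shown, set against an exact interval about 32 points wide (61.5 − 29.3 = 32.2) for 18/40. The contrast of 80% with 10% shows what could be hidden and is not a forecast.

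A descriptive baseline-by-week-4 ISGA table, with counts and exact intervals for each entry grade, is a reasonable optional addition to the report, provided the width of those intervals is acknowledged.

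### The treatment-emergent adverse event outcome is drawn from a four-item local tolerability assessment, two items of which are also disease signs, and is not linked to the adverse event record

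*Combined protocol and SAP*

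**What the plan says.** Safety Outcome Measures opens with the treatment-emergent outcome and names its source: "Incidence, severity, and type of treatment-emergent adverse events will be collected via the local tolerability assessment". Adverse events appear again in the same list as a separate item, with no metric and no reference to the first.

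Procedures describes the tolerability assessment: "We will assess for redness, pain, burning, and scaling at the application site". On timing it says: "Provider and Patient local tolerability assessment will be collected at Baseline (before medication application) week 1, 2, and 4". Subjects are told to apply the ointment to the affected facial skin.

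Background says of the disease: "It presents as an erythematous, thin scaly patch with a greasy sandpaper texture". Inclusion criterion 5 requires: "Mild to moderate seborrheic dermatitis on the face with an ISGA of 2 or 3 at baseline".

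Procedures also provides for a general collection: "Adverse events will be collected from after the informed consent document is signed through week 4". The Schedule of Events has an adverse event row separate from the tolerability row. Both are marked at baseline and weeks 1, 2 and 4.

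The Statistical Analysis section specifies descriptive statistics only. No section defines treatment-emergent, and none says when a tolerability finding is also an adverse event.

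**The concern.** The incidence, severity and type of treatment-emergent adverse events normally cover everything that starts or worsens after the first dose, at any body site. Here the outcome is tied to an instrument described by four application-site items. Followed as written, this has two consequences.

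- **Coverage.** A headache, an infection, or a local reaction outside the four items has no place in the named source.
- **Specificity.** Redness and scaling are what the disease looks like, and the treated skin is the diseased skin. Unless scores are compared with the pre-application score, disease already present can be counted as an event.

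The title names safety as well as efficacy, and the plan aims at publication. A reader of the report would take the treatment-emergent figures as the main safety summary, and those figures would not have their usual meaning.

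**Working it through.** The plan gives no figure to reproduce for this outcome. The check sets the sections side by side and then sizes one consequence under assumed rates.

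**Items in the named source (Procedures against Background)**

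| Item | Application site only? | Also described as a disease sign? |
|---|---|---|
| Redness | yes | yes (erythematous patch) |
| Scaling | yes | yes (scaly patch) |
| Pain | yes | not named |
| Burning | yes | not named |

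All 4 items are local, none can hold a non-local event, and 2 of the 4 overlap with the disease.

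**Timing (Schedule of Events)**

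- Tolerability row: baseline, weeks 1, 2 and 4. That is 1 assessment before application and 3 after.
- Adverse event row: the same 4 visits.
- ISGA, "Seborrheic dermatitis grading scale" and photography: each is also marked at all 4 of these visits.

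The data for a baseline comparison, and for reading redness and scaling beside the state of the disease, are therefore already scheduled. The plan does not say that either comparison will be made.

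**Collection window.** General adverse event collection starts at signed consent, which the schedule places at screening. First application comes after the baseline tolerability assessment. The record can therefore hold both pre-treatment and on-treatment events, and no onset rule separates them.

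**Size of the coverage gap.** N = 40 (Study Design). The documents give no event rate, so 5%, 10% and 20% over 4 weeks are assumptions, with subjects taken as independent.

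Expected subjects with a non-local event = 40 × p. Chance of at least one = 1 − (1 − p)^40.

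| Assumed p | Expected subjects | Chance of at least one |
|---|---|---|
| 0.05 | 40 × 0.05 = 2 | 1 − 0.95^40 = 0.871 |
| 0.10 | 40 × 0.10 = 4 | 1 − 0.90^40 = 0.985 |
| 0.20 | 40 × 0.20 = 8 | 1 − 0.80^40 = 0.9999 |

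These are subjects whose events would be absent from the treatment-emergent outcome as described. They would still be in the trial's adverse event data.

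No comparable figure is offered for disease counted as events. The number would depend on how redness and scaling are scored at each of weeks 1, 2 and 4, and the documents do not give this. The week 4 ISGA response would not bound it either: a score of 1 means only almost clear, and a subject clear at week 4 could have scored redness earlier.

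**The case against.** The strongest reply is that the safety list divides the work sensibly: the first item covers local reactions to a topical product, and the separate adverse event item covers everything else. On that reading the fault is a loose label, and the figures above show only which heading an event falls under. The last part is correct. But the label then needs changing, and no outcome is left that reports the incidence, severity and type of treatment-emergent events in general.

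A second reply is that the term treatment-emergent, together with a score taken before application, already implies comparison with baseline. This is fair. A reader might infer that every subject, having disease at entry, would be counted as having an event. The documents do not support that: redness present before the first application is not treatment-emergent in any ordinary sense, and no section says raw scores will be counted. What stands is that the comparison is not written down.

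A reader might also infer that non-local adverse events go unrecorded. The documents contradict this, since they are collected from consent through week 4 and listed as a safety outcome.

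Finally, neither the tolerability form nor the adverse event record is reproduced. Either may hold more items, severity grades or onset dates. The criticism of coverage applies to the assessment as described.

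**Conclusion.** The point holds as a defect in how one safety outcome is sourced and defined. The plan names a source that, as described, has no item for non-local events and shares two of its four items with the disease at the treated site. It does not link the outcome to the broader adverse event record, which itself begins before treatment.

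The effect is minor. The analysis is descriptive, the only stated objective is efficacy, no primary result changes, and the general adverse event outcome limits the loss. The 2, 4 or 8 of 40 rest on assumed rates and independence and measure misplacement, not missing data. The conclusion itself does not depend on them: it follows from the text. It is worth correcting because the correction is cheap and the treatment-emergent summary is what readers will quote.

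**What to change.** 1. Derive the incidence, severity and type of treatment-emergent adverse events from the existing adverse event record, counting events with onset or worsening after the first application. List events between consent and first application separately.
2. Report the four tolerability items as a separate local tolerability outcome, as change from each subject's pre-application score at weeks 1, 2 and 4, with pain and burning shown apart from redness and scaling. State that a single arm cannot fully separate irritation from the course of the disease.
3. State when a tolerability finding is also entered in the adverse event record, for example on worsening from the pre-application score. Without this rule, step 1 could drop new local reactions noted only on the tolerability form from the treatment-emergent count.

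The cost is small: a few sentences in the plan, onset date and severity fields on the adverse event record if it lacks them, and one descriptive table of at most 2 raters × 4 items × 3 post-baseline visits = 24 change summaries. No visit is added, since both assessments already take place at the same 4 visits.

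### Is a listed safety outcome, vital signs, left uncollected because no schedule row or procedure names it?

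*Combined protocol and SAP*

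**What the plan says.** Vital signs occur twice in the combined protocol and SAP. The Safety Outcome Measures list has the entry "Vital signs, clinical assessments, and laboratory test results", without a visit or a method. Exclusion criterion 6 bars subjects with "Any clinically relevant abnormal vital signs or findings on the physical examination" that the investigator thinks might interfere with the assessments.

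Under Procedures, timing is given in words for several safety items. The sentence on tolerability is "Provider and Patient local tolerability assessment will be collected at Baseline (before medication application) week 1, 2, and 4". Adverse events have their own sentence, "Adverse events will be collected from after the informed consent document is signed through week 4", and a further one covers other drugs that subjects take, namely "Concomitant medications will be collected from screening to week 4". Laboratory work is limited: "Other than Urine Pregnancy Tests for women of childbearing potential, no other laboratory evaluations are necessary". The text then hands over to the Schedule of Events: "Procedures are listed in table below". That table has 13 rows and 5 visits (screening, baseline, weeks 1, 2 and 4). It has a physical examination row (PE) marked at screening and week 4, and an eligibility row marked at screening and baseline. It has no vital-signs row, and the content of the PE is not described anywhere.

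On analysis, the plan says "As this is a proof of concept, open label study, descriptive statistics will be utilized".

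**The concern.** A safety outcome needs readings after treatment starts. If the schedule is taken as the complete list of procedures, staff could follow it to the letter and finish the study without a recorded vital sign on treatment, which would leave a named outcome with nothing to summarise. The wording of exclusion 6 adds to the doubt: it mentions vital signs beside physical examination findings, as if they might be two separate things, so the PE row does not plainly cover them. The visit at which the reading for exclusion 6 is taken is also not stated. The contrast with tolerability, adverse events and concomitant medications, each of which has both a row and a sentence, makes the silence look like an oversight.

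**Working it through.** The plan gives no figure to reproduce here, so the check sets the safety list against the Procedures text and the schedule. Splitting the list's four bullets into six items gives the table below. There are 3 post-baseline visits: weeks 1, 2 and 4.

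| Safety item | Named in a row or a Procedures sentence? | Post-baseline visits if the nearest row is accepted |
|---|---|---|
| Treatment-emergent events via local tolerability | Yes | 3 of 3 |
| Vital signs | No | 1 of 3, through the PE (week 4) |
| Clinical assessments | No | 1 of 3 through the PE, or 3 of 3 through ISGA and the grading scale |
| Laboratory results | Yes, as the urine pregnancy test | 1 of 3 (week 4), women of childbearing potential only |
| Concomitant medication | Yes | 3 of 3 |
| Adverse events | Yes | 3 of 3 |

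**One rule for all items.** If an item must be named, two of the six fail (vital signs and clinical assessments) and 6 - 2 = 4 pass. If the nearest suitable row is accepted, none fails. Vital signs stand out alone only if clinical assessments may borrow the PE row and vital signs may not. The text gives no ground for that difference.

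**Exclusion 6.** Eligibility is checked at screening and baseline, so the criterion has two stated visits. The PE is done at screening, so a reading taken with it would be available at both checks. Only the visit of the reading itself is unstated. The criterion rests on investigator opinion and sets no numerical limit that a missing reading would leave unapplied.

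**Contradiction or silence.** No passage says that vital signs are not taken, and none says that the PE leaves them out. The passages are compatible, and what is missing is a description of the PE.

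**What is at stake in numbers.**

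- If the PE includes vital signs: 40 subjects x 2 visits = 80 sets of readings at most, assuming that all 40 reach week 4. That is one pre-treatment and one end-of-treatment set per subject, enough for a descriptive summary of change.
- If it does not: 0 of 3 post-baseline visits have readings, and one descriptive summary is lost. Adverse events, tolerability and concomitant medications are still recorded at 3 of 3 post-baseline visits.
- Under either reading the ISGA primary outcome and the itch secondary outcome are unchanged, because neither uses vital signs.

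**The case for a change.** The strongest case for a change is that a descriptive analysis still needs data, and the plan does not guarantee any for this item. The PE may cover vital signs, but the document never says so, and exclusion 6 can be read as treating them as separate from the examination. The eligibility row implies at most a check before treatment and gives nothing on treatment. One row or one sentence at two existing visits would settle the matter at almost no cost.

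Part of this stands. The words are absent from the Procedures text and the schedule, and a strictly literal site could omit the readings. An asymptomatic change in vital signs might then go unseen, since adverse event reporting would not necessarily catch it. What does not stand is the step from there to a defect in the plan. Naming vital signs beside examination findings does not show that the PE excludes them, and taking them with a physical examination is the ordinary reading. A low cost is not by itself a reason for a change. The added sentence would record what staff would probably do anyway, and no conclusion of the study depends on it.

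**Conclusion.** The factual core holds: vital signs are a listed safety outcome and are used for eligibility, and no schedule row or Procedures sentence names them. It does not amount to an inconsistency that needs correction. It is a gap in detail that staff can fill sensibly from the PE at screening and week 4, and the eligibility check that uses vital signs already has its visits.

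The size is at most one descriptive safety summary in 40 subjects. The study is open label and descriptive, and no threshold, stopping rule or decision uses the readings. The main safety information comes from items collected at every post-baseline visit.

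This rests on two assumptions: that the PE is carried out in the ordinary way with vital signs recorded, and that no conclusion will be drawn from vital signs beyond description. If the first fails, the report would have to say that vital signs were not recorded on treatment, and the study's other results would remain sound.

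### Does calling 40 subjects adequate, with no precision target and no rule for a missing ISGA rating, leave the primary result undetermined?

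*Combined protocol and SAP*

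**What the plan says.** The Statistical Analysis section sets the scope: "As this is a proof of concept, open label study, descriptive statistics will be utilized". On size, Study Design states "40 eligible subjects will be enrolled", and Statistical Analysis adds "The sample size was based known patient population and pragmatic considerations and is adequate to characterize anticipated observed effects".

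The Primary Outcome Measure defines the response: "A 0 or 1 (clear or almost clear) on the ISGA would be considered a treatment success". It does not name the visit. Treatment lasts 4 weeks (Background and Procedures), and the Schedule of Events takes the ISGA at screening, baseline and weeks 1, 2 and 4. Inclusion criterion 5 requires "Mild to moderate seborrheic dermatitis on the face with an ISGA of 2 or 3 at baseline", so nobody is a success at entry.

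Two entry criteria bear on completion. Inclusion criterion 3 asks that subjects can complete the study and follow its instructions. Exclusion criterion 11 removes anyone "Considered unable or unlikely to attend the necessary visits". Both are screens, and neither says how to count a subject who is enrolled and later has no rating. No analysis set, replacement rule or missing-data rule appears anywhere in the document.

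**The concern.** The word adequate implies a standard, and the plan states none: no anticipated success rate, no interval width, no allowance for loss. A reader cannot check the claim.

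The more practical point is the denominator. At least three analyses fit the text: successes among those rated at week 4; successes among all enrolled, with a missing rating counted as not a success; and the last available rating, since earlier ISGA scores exist. The same data can give a different proportion under each.

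The study is open label and describes no comparator, so outcomes are visible throughout and this proportion is its only primary result. Tolerability could also matter, because the Procedures section says "We will assess for redness, pain, burning, and scaling at the application site". If subjects left because of such reactions and were not rated, the rated-only figure would omit them and be higher than one that counts them as failures. What would be at stake is a more favourable choice of denominator after the results are known.

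**Working it through.** **Inputs from the document.** 40 to be enrolled (Study Design); success is ISGA 0 or 1 (Primary Outcome Measure); baseline ISGA 2 or 3 (inclusion criterion 5); ratings at weeks 1, 2 and 4 (Schedule of Events).

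**Assumptions.** The document gives no success rate and no dropout rate. Let x be the number of week 4 successes and m the number with no week 4 rating, with m = 0, 2, 4 or 6. Week 4 as the primary visit is inferred from the treatment period and the last scheduled visit.

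**Can 40 be reproduced?** No, because no input is stated. Working backwards with n = z² p(1 − p)/h², p = 0.5 and 95% confidence, the required n is 97 for a half-width h of 10 points, 43 for 15 points, 40 for 15.5 points and 25 for 20 points. So 40 suits some targets and not others. This neither supports nor refutes the word adequate.

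**Precision that 40 gives if all are rated.** Exact (Clopper-Pearson) 95% interval width: 20.9 points at 10% or 90%, 26.6 at 20% or 80%, 30.0 at 30% or 70%, and at most 32.4 at 50% (20/40: 33.8 to 66.2).

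**Effect of the denominator.** Rated-only = x/(40 − m). Missing as not a success = x/40. The difference is [x/(40 − m)] × (m/40), which is never negative.

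| m | x | Rated-only | Missing as not a success | Difference (points) |
|---|---|---|---|---|
| 0 | 20 | 20/40 = 50.0% | 20/40 = 50.0% | 0 |
| 2 | 19 | 19/38 = 50.0% | 19/40 = 47.5% | 2.5 |
| 4 | 18 | 18/36 = 50.0% | 18/40 = 45.0% | 5.0 |
| 6 | 10 | 10/34 = 29.4% | 10/40 = 25.0% | 4.4 |
| 6 | 17 | 17/34 = 50.0% | 17/40 = 42.5% | 7.5 |
| 6 | 24 | 24/34 = 70.6% | 24/40 = 60.0% | 10.6 |

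**Last available rating.** With x = 17 and m = 6, the result lies between 17/40 = 42.5% and (17 + 6)/40 = 57.5%, depending on the earlier ratings of the six. A subject with only a baseline rating counts as a non-success, since baseline is 2 or 3.

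**Against sampling error.** For m = 6 and x = 17, the exact 95% intervals are 32.4 to 67.6 (rated-only, width 35.1 before rounding the limits) and 27.0 to 59.1 (all 40, width 32.1). They overlap from 32.4 to 59.1. The 7.5-point difference is under a quarter of either width (7.5/32.1 = 0.23).

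**The case for a change.** The strongest case for a change is that a descriptive proportion still needs a numerator and a denominator, and this plan fixes neither the visit nor the denominator. Visit choice could alter the result even with complete data, because the ISGA is also taken at weeks 1 and 2. In an open-label study, nothing hides the consequence of each choice. The plan itself aims for data strong enough for a leading journal, and fixing the rule in advance would cost a few sentences and no extra patients or visits.

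Part of this stands. The details are absent, redaction does not explain it, and the percentages above are correct. What does not follow is that the plan yields a wrong result. It states no rule that misleads. Week 4 is the end of treatment and the last visit, so it is the reading an analyst would take. Rated-only and missing-as-failure are both ordinary choices with known drawbacks: the first can flatter if losses are related to treatment, and the second understates if visits are missed for unrelated reasons. A report showing the number of successes, the number rated and the number enrolled lets a reader move from one to the other.

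The tolerability argument is conditional. The plan describes an assessment of local reactions, not departures because of them, and a subject who stops applying the ointment may still attend and be rated.

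On sample size, the plan openly calls its basis pragmatic. With no hypothesis test, success threshold or claimed power, 40 has no criterion to fail. Replacing the word adequate with a set of interval widths would be a matter of presentation.

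**Conclusion.** No change to the plan follows. The missing visit, denominator and missing-rating rule are gaps in detail that analysts can fill sensibly, and 40 is a stated pragmatic choice that has not been shown to be wrong.

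If half of those rated are successes, the two main readings differ by 0 points with nobody missing, 2.5 with 2 missing, 5.0 with 4 and 7.5 with 6. With 6 missing, other success counts shown give 4.4 to 10.6 points. All of these rest on assumed counts. Six missing is 15% of 40, and nothing in the document supports or excludes it for a single-site study with 4 weeks of treatment and three post-baseline visits. Since the plan attaches no decision to the proportion, none of these differences alters a stated conclusion.
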